## 1.0 Objectives

### 1.1 Study Objectives

The proposed study aims to evaluate the acute vascular effects of dietary nitrates on the peripheral and central circulation, both at rest and during physiological stress in older women.

**Aim 1:** To determine the blood pressure-lowering effects of acute dietary nitrate supplementation in postmenopausal women.

*Hypothesis: A one time dose(140 mL) of concentrated beetroot juice will lower resting arterial stiffness, brachial artery blood pressure, and/or derived aortic blood pressure in postmenopausal women with and without hypertension.*

**Aim 2:** To determine the effects of acute dietary nitrate supplementation on myogenic vasoconstriction of leg blood vessels during simulated postural stress.

*Hypothesis:* A one time dose (140 mL) of concentrated beetroot juice will reduce the amount of vasoconstriction in leg blood vessels exposed to graded increases in vascular transmural pressure (i.e., single leg suction) in postmenopausal women with and without hypertension.

**Aim 3.** To determine the effects of acute dietary nitrate supplementation on the control of blood pressure responses during exercise.

*Hypothesis:* A one time dose (140 mL) of concentrated beetroot juice will lower blood pressure responses to static arm and dynamic leg exercise. Beetroot juice will reduce the concentration of blood pressure-raising metabolites in exercising muscles through improvements in muscle perfusion and/or reductions in the metabolic cost of muscle contraction.

### **1.2 Primary Study Endpoints**

The primary endpoints of this study are blood pressure, arterial wave reflection characteristics, and muscle metabolic responses. These responses will be measured at rest and during exercises in postmenopausal women before and after beetroot juice consumption.

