## **7.0 Study Design and Procedures**

### **7.1 Study Design**

The proposed study will examine age- and dietary nitrate supplementation induced effects on blood pressure and other cardiovascular variables in women. To do so, we will recruit groups of healthy premenopausal (18 – 35 yrs) and postmenopausal (55 – 80 yrs) women from State College, Pennsylvania and surrounding communities. A strength of our study design will be: 1) double-blind placebo-controlled study intervention and 2) our careful control for overt diseases and disease risk factors, medication use, and extremes in physical activity/inactivity to minimize their potential confounding influence on our study outcomes.

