- 6) Dynamic Leg Exercise (DLE) - While seated in semi recumbent position, participants will have one leg placed in a knee-exercise device. We will then passively move their leg for them in a kicking motion while a cuff is inflated on their upper thigh. Participants will then perform 9 minutes of active knee extensions (3 min no resistance; 6 minutes moderate resistance) with the thigh cuff deflated, followed by 3 minutes of rest with the cuff inflated. Leg blood flow will be measured by Doppler ultrasound, and muscle pH will be measured by a near-infrared sensor placed over the skin on the thigh.

Premenopausal Visit 3. Estradiol assessment visit (Premenopausal women only). – Subjects will be asked to return to the lab on one day between days 9-11 of their menstrual cycle for a blood draw. Approximately 10 ml of blood will be taken from an arm vein during this visit. This blood draw will be used to assess their serum estradiol content at that point in their cycle. The results of this test will be used to schedule their second experimental visit (Premenopausal visit 4). Subject visits will be scheduled so that no more than 2 blood draws occur in a given week.

Postmenopausal Visit 3. Beetroot Juice Study Visit (Postmenopausal women only) - A CRC nurse will take a blood sample from an arm vein. Participants will then undergo measures of HR, PWV, and BP. Next, participants will consume 140 mL (9.5 tablespoons) of either nitrate-rich beet juice or beet juice with nitrates removed with a small snack, and will remain at the CRC

for 1.5 hours. 1.5 hours after consuming the beet juice, a second blood sample will be taken and the participants will undergo measures of HR, PWV, BP, LS, SHE, and DLE. Once these measurements are completed, a third blood sample will be taken.

Premenopausal Visit 4. Experimental Study Visit- Procedures will be identical to those during Premenopausal Visit 3.

Postmenopausal Visit 4. Beetroot Juice Study Visit (Postmenopausal women only) - Procedures will be identical to those during visit 3 except that participants will consume whichever drink supplement they did not receive during visit 3.

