#### **7.4.5 Blinding of the Test Article**

Treatment order will be randomly assigned to participants by Clinical Research Center (CRC) staff using computer-based mathematical software (Microsoft Excel). The generated list that determines each participants treatment order will be kept in a secure location in the CRC which cannot be accessed directly by research team members.

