## **9.2 Statistical methods**

Comparisons of arterial stiffness and arterial wave characteristics between the placebo and beetroot juice visits will be performed using paired t-tests. Paired t-tests will also be performed to compare plasma nitrate and nitrite concentrations between the two visits for all data points. Two-factor ANOVA with repeated measures will be used to assess blood pressure lowering effects of beetroot juice at rest and during exercise in postmenopausal women. A value of  $p < 0.05$  will be considered statistically significant for all experiments.

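### Section 1.2 words the primary endpoints as before and after beetroot juice without naming the placebo contrast, and for exercise measures the only 'before' on schedule is the unrandomised Visit 2

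*Combined protocol and SAP*

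**What the plan says.** **Endpoints (1.2).** "The primary endpoints of this study are blood pressure, arterial wave reflection characteristics, and muscle metabolic responses". They are to be measured at rest and during exercise "in postmenopausal women before and after beetroot juice consumption". Placebo is not mentioned, and neither a change score nor a comparator is defined.

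**Design (7.1, 7.2.2, 7.4.5).** The trial is described as a "double-blind placebo-controlled study intervention". "Treatment order will be randomly assigned to participants", and at Visit 4 postmenopausal "participants will consume whichever drink supplement they did not receive during visit 3".

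**Schedule (7.2.2).** On the two drink visits a blood sample is taken first. Then: "Participants will then undergo measures of HR, PWV, and BP". The drink follows. After 1.5 hours these measures are repeated, and leg suction, handgrip and leg exercise are done for the only time that day. Visit 2, labelled the baseline visit, includes the full set of tests with no drink. It comes before Visits 3 and 4, and 7.3 requires at least 5 days between these visits.

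**Analysis (9.2).** "Comparisons of arterial stiffness and arterial wave characteristics between the placebo and beetroot juice visits" are made by paired t-test. Blood pressure, at rest and during exercise, is assessed by "Two-factor ANOVA with repeated measures", with neither the factors nor the tested term named. No test is given for the muscle metabolic responses.

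**The concern.** A before-after comparison credits the juice with everything else that changes between the two measurements. At rest, that is 1.5 hours in the research centre and a snack. For exercise, if Visit 2 serves as the 'before', it is habituation to the laboratory and a repeat of the same handgrip and leg tests on a later day. The placebo visit and the randomised order are there to remove these influences, but they do so only if the analysis uses them.

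As the text stands, an analyst could report as the primary blood pressure result a fall on the beetroot visit, a difference from Visit 2, or a difference from placebo, and could argue that each complies. Only the last is protected by randomisation. For stiffness the contrast is the right one, but a same-day pre-drink measurement that could sharpen it is not used.

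**Working it through.** The plan gives no figure of its own on this point, so the check is mainly of one section against another.

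**1. Which contrasts the schedule allows**

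| Measure | Visit 2 (no drink) | Visits 3/4, pre-drink | Visits 3/4, post-drink |
|---|---|---|---|
| Resting BP, PWV | yes | yes | yes |
| Leg suction | yes | no | yes |
| Handgrip | yes | no | yes |
| Leg exercise | yes | no | yes |

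The before-and-after measurement that 1.2 describes can be made on the same day at rest, but not during exercise.

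**2. What each contrast estimates**

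Let τ be the effect of nitrate, δ the change over a drink visit that occurs with either drink, and h the shift from Visit 2 to the later visits.

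- Beetroot visit, post minus pre: τ + δ.
- Beetroot change minus placebo change: (τ + δ) − δ = τ.
- Exercise, post-beetroot minus Visit 2: τ + h, where h also absorbs any effect of having had a drink.
- Exercise, post-beetroot minus post-placebo: τ. A shift between Visits 3 and 4 is balanced in expectation by the random order.

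If Visit 2 is subtracted from both drink visits it drops out: (B − V2) − (P − V2) = B − P. Visit 2 therefore adds nothing to the placebo-controlled exercise contrast.

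**3. What the ANOVA sentence allows**

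At least three pairs of factors fit two-factor repeated measures: drink × time, drink × exercise stage, and time × hypertension group. The first two contain placebo and the third does not. Section 9.1 describes the sample size as being for a within-between comparison, so the third cannot be ruled out.

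**4. Size, as an illustration only**

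Suppose τ = 0 and the test is a two-sided paired t-test of pre against post on the beetroot visit alone. The noncentrality is λ = (δ/SD) × √n, and the rejection probability is P(|t′| > t crit) on n − 1 degrees of freedom. I take n = 12 as two postmenopausal groups of the 6 given in 9.1. The documents do not say how many of the 24 completers in section 16.0 are postmenopausal. Drift and SD of change are assumptions.

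Example: δ = 3, SD = 6, n = 12 gives λ = 0.5 × 3.464 = 1.73. With t crit = 2.201 on 11 degrees of freedom, the probability is 0.35.

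| Drift (mmHg) | n = 12, SD 6 | n = 12, SD 8 | n = 6, SD 6 | n = 6, SD 8 |
|---|---|---|---|---|
| 1 | 8% | 7% | 6% | 6% |
| 2 | 18% | 12% | 10% | 8% |
| 3 | 35% | 22% | 17% | 12% |
| 4 | 56% | 35% | 27% | 17% |
| 5 | 75% | 51% | 38% | 24% |

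Under the same drift on both visits, beetroot minus placebo stays at 5%.

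**5. What the pre-drink value can add at rest**

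Let r be the correlation between the pre-drink difference and the post-drink difference (beetroot minus placebo, within woman). Adjustment multiplies the variance of the post-drink difference by about 1 − r², less a small loss for one degree of freedom. The documents give no r. For assumed r of 0, 0.25, 0.5 and 0.75, the factor is 1, 0.94, 0.75 and 0.44.

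**The case against.** The tempting stronger reading is that the primary endpoint is a before-after change instead of beetroot versus placebo, so that the plan throws its control away. The documents do not support that.

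- Section 1.2 states when measurements are taken. It defines no test.
- Section 7.4.6.3 calls the placebo a form of beetroot juice, and 7.2.2 gives both drink visits the same beetroot title, so the phrase in 1.2 can be read to cover both visits.
- Section 9.2 does set placebo against beetroot for stiffness, wave characteristics and plasma nitrate and nitrite.
- Resting blood pressure is taken before and after each drink, and drink × time is a natural pair of factors for those data.
- The lack of a pre-drink exercise test is not a flaw in itself. In a randomised crossover, post-drink against post-drink is valid without a same-day baseline.
- No section says that Visit 2 will be the comparator for the juice effect.
- The false-positive figures model a test that 9.2 does not state, on values the documents do not give.

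All of this stands, and it limits the point to what is left open. It does not close the gap: 1.2 speaks of before and after during exercise, the schedule offers only Visit 2 as that 'before', and nothing in 9.2 excludes its use or commits the blood pressure ANOVA to placebo.

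**Conclusion.** The point holds as a gap in specification that leaves room for a biased primary comparison. It is not evidence that such a comparison is planned. Three things are established from the text alone: 1.2 does not name the placebo contrast; a same-day before-after comparison is impossible for leg suction, handgrip and leg exercise; and the ANOVA factors for blood pressure are unnamed. A fourth concerns precision: the between-visit t-test for stiffness leaves out the pre-drink PWV.

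The size is not determinable. The illustrative false-positive rates with 12 women run from about 7% (drift 1 mmHg, SD 8) to 75% (drift 5 mmHg, SD 6), and are lower with 6. They apply only if a beetroot-only before-after test were used, and rest on assumed drift, SD and n. The conclusion does not depend on them, because drift common to both drink visits cancels in beetroot minus placebo and does not cancel in before-after.

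**What to change.** 1. **Section 1.2.** State the primary contrast as the within-woman difference between nitrate-rich and nitrate-removed juice on Visits 3 and 4.
2. **Exercise measures and leg suction.** Compare post-drink with post-drink. Say that Visit 2 is not the 'before' for the juice effect, and keep it for the age comparison in 1.3 and for familiarisation.
3. **Resting blood pressure and PWV.** Adjust the beetroot-minus-placebo difference in post-drink values for the corresponding difference in same-visit pre-drink values.
4. **Section 9.2.** Name the factors and the tested term: drink × time at rest, drink during exercise. In a two-by-two layout, drink × time is the paired test of the difference in changes, which fixes the coefficient of the pre-drink difference at 1. The adjustment in item 3 estimates that coefficient. State in advance which of the two is the primary result.

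The cost is rewording in two sections and one degree of freedom for the baseline adjustment. Every measurement needed is already scheduled, so no new data are required.

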### **1.3 Secondary Study Endpoints**

Blood pressure, arterial wave reflection characteristics, and muscle metabolic responses will also be measured in pre-menopausal women (visit 2 only) to allow age group comparison of these variables.

## **2.0 Background**

### **2.1 Scientific Background and Gaps**

High blood pressure is a major risk factor for cardiovascular morbidity and mortality. Following menopause, women are more likely to develop high blood pressure. Postmenopausal women also experience greater increases in blood pressure during physical activity/exercise, and are more susceptible to blood pressure-related complications compared with either premenopausal women or men of a similar age. In addition to experiencing a greater risk associated with elevated blood pressure, blood pressure management is also relatively poor in women after menopause; more than half of postmenopausal women with hypertension do not have their blood pressure successfully treated. Therefore, there is a clinical need to investigate novel interventions aimed at improving blood pressure regulation in postmenopausal women both at rest and in response to physical stresses encountered during activities of daily living (e.g., posture, carrying objects, &ambulation).

### **2.2 Previous Data**

Nitric oxide (NO) plays a key contributing role in the modulation of blood vessel tone at rest and under conditions of increased metabolic demand, such as exercise . As a result, there has been a growing interest in the use of dietary interventions that increase bioavailable NO as both cardiovascular health-promoting  and ergogenic aids . In particular, dietary supplementation with inorganic salts or high-nitrate containing foods (e.g., beetroot juice) has recently grown in popularity for its potential blood pressure-lowering and aerobic exercise performance-enhancing effects. With regard to the former function, numerous investigators have shown the reduction in resting blood pressure with beetroot juice consumption in healthy adults . However, only two publications reported blood pressure lowering effects of beetroot juice in older adults , and no study has investigated the influence of dietary nitrate supplementation on exercise pressor response in postmenopausal women who are known to have reduced nitric oxide bioavailability.

### **2.3 Study Rationale**

Dietary nitrate supplementation is a natural means of increasing the molecule nitric oxide in the body, and an emerging intervention for improving cardiovascular health and exercise performance. Specifically, beetroot juice (a nitrate-rich food supplement) has been shown to have both vasodilatory and peripheral blood pressure lowering, as well as muscle metabolic effects. However, the effectiveness of dietary nitrates to lower resting blood pressure in postmenopausal women, as well as their ability to modulate blood pressure responses to physical stress have not been adequately explored. Therefore the purpose of the present study is to examine the effectiveness of an acute dose of nitrate-rich beetroot juice to lower resting blood pressure, arterial stiffness, and blood pressure responses to physical stress in postmenopausal women with and without hypertension.

## **3.0 Inclusion and Exclusion Criteria**

### **3.1 Inclusion Criteria**

- 1) Premenopausal women between the ages of 18 and 35 years old with resting blood pressure < 140/90 mm Hg, and who have had regular menstrual cycles for the previous 6 months.
- 2) Postmenopausal women between the ages of 55 and 80 years old.

### **3.2 Exclusion Criteria**

- 1) Individuals with any overt cardiovascular, metabolic, hematologic, pulmonary, renal, musculoskeletal, and/or neurological disease(s).
- 2) Users of any tobacco and/or nicotine products (smokers, chewing tobacco, nicotine-containing patches/gum, smokeless cigarettes)
- 3) Individuals with a BMI > 35
- 4) Individuals with resting blood pressure > or = 160/100 mm Hg
- 5) Individuals with high blood lipids (total cholesterol > or = 240 mg/dl, LDL > or = 160 mg/dl, triglycerides > or = 200 mg/dl)
- 6) Premenopausal women with hyperglycemia (fasting glucose > or = 110 mg/dl)
- 7) Postmenopausal women with hyperglycemia (fasting glucose > or = 110 mg/dl and HbA1c >6.0%).
- 8) Individuals taking any of the following medications:
  - a. blood pressure lowering medication (e.g., beta blockers, ACE inhibitors, angiotensin antagonists, calcium channel blockers, diuretics)
  - b. lipid- lowering medication (e.g., statins)
  - c. nitrates (e.g. nitroglycerin) for angina
  - d. phosphodiesterase inhibitors (e.g., Viagra)
  - e. anti-Inflammatory drugs
- 9) Individuals taking hormone replacement therapy, hormone-based contraceptives.
- 10) Premenopausal women who are pregnant
- 11) Individuals with a history of orthopedic problems including hip or knee surgery that could cause significant knee pain during the step test or knee extension exercise.

### **3.3 Early Withdrawal of Subjects**

#### **3.3.1 Criteria for removal from study**

Any subjects experiencing a serious adverse event felt to be related to the study intervention (beetroot juice supplementation) or procedures will be withdrawn from the study. Also, if a subject withdraws her consent to participate in the study or authorization to use her protected health information, she will be withdrawn from the study.

### **3.3.2 Follow-up for withdrawn subjects**

A subject who decides to discontinue participate in this study will immediately be withdrawn from the study. Within 5 days, one of the study investigators will contact the subject for a follow-up interview. Subject who withdraw withdrawn may be replaced, at the discretion of the principal investigator.

## **4.0 Recruitment Methods**

### **4.1 Identification of subjects**

Premenopausal women will be recruited from the Penn State (University Park campus) student population and State College community by fliers and advertisements. Fliers will contain basic information about the study, as well as contact information for study personnel in the Vascular Aging and Exercise Laboratory (201 Noll Lab). Potential participants who show interest in the study by contacting study personnel will be sent an informed consent form in the mail with instructions to contact the one of the study investigators if she has any questions or would like to schedule a visit to Noll Lab for the screening and familiarization visit.

Postmenopausal women (both normotensive and hypertensive subjects) will be patients of the Penn State Hershey Medical Group in State College (i.e., the physician co-investigators listed on this protocol) or members of the State College community. Patients who meet the study's inclusion/exclusion criteria may be identified by their physician during the patient's routine visit to physician's medical office, and informed them of their potential eligibility for a research study at Penn State. They will also be provided with a flier that contains basic information about the study, as well as contact information for study personnel in the Vascular Aging and Exercise Laboratory (201 Noll Lab). Potential participants who show interest in the study by contacting Noll Lab personnel will be sent an informed consent form in the mail with instructions to contact the one of study investigators if she has any questions or would like to schedule a visit to Noll Lab to obtain informed consent. Postmenopausal women will also be recruited from the State College community by fliers and advertisements. Fliers will contain basic information about the study, as well as contact information for study personnel in the Vascular Aging and Exercise Laboratory (201 Noll Lab).

In addition to fliers and direct recruitment methods, a database search in the Penn State Hershey electronic medical record will be requested by [name], Penn State Hershey Medical Group (PSHMG) research coordinator. Search criteria will include postmenopausal women ages 55-80 seen by a PSHMG Family and Community (F&C) medicine physician between July 1, 2013 to present, non-smoker, BP less than 160/100mmHg with a BMI<35. Medications will be reviewed to exclude anyone currently taking lipid or blood pressure lowering medication or hormone replacement therapy. After potential subjects are identified, [name] will mail study recruitment letters, signed by one of the 4 physician co-investigators, to the patients. [name] will conduct a follow up phone call within 1-2 weeks of initial contact being made to answer any questions potential subjects may have. If the patient is interested in participating in the study, she will be asked to call the Vascular Aging and Exercise lab (201 Noll Lab) for further information. Potential participants who originally received a recruitment letter from PSHMG will not be contacted by phone since the original letter indicated that there would be no further contact.

## **4.2 Recruitment process**

Members of the Vascular Aging and Exercise Laboratory will answer phone calls (office phone) or emails from potential participants. During these exchanges prospective participants may ask any questions regarding the study and/or schedule a visit to complete informed consent and screening process.

## **4.3 Recruitment materials**

- Flyers/posters
- Posting on Website, Research At Penn State ([www.research.psu.edu/volunteer](http://www.research.psu.edu/volunteer))
- Database search in Penn State Hershey Electronic Medical Records
- Recruitment letters sent out by [name]

